##### 4.1 Analysis Sets

The following analysis sets will be used for the analysis of the data after full close-out of the COMPASS trial after LTOLE.

- **Intention-to-treat Analysis Set (ITT):**  
The intention-to-treat analysis set, also termed full analysis set in the International Conference on Harmonization (ICH) E9 guideline, includes all subjects randomized to antithrombotic study treatment for the initial study part. The ITT set comprises both subjects randomized to pantoprazole/placebo and subjects not randomized to pantoprazole/placebo.

- Long-Term Open-Label Extension ITT Analysis Set (LTOLE ITT):  
The LTOLE ITT analysis set comprises all subjects who completed LTOLE initiation visit (LTOLE initiation visit date entered).
- Long-Term Open-Label Extension Safety Analysis Set (LTOLE SAF):  
The LTOLE Safety analysis set will include all subjects who completed LTOLE initiation visit and who received at least one dose of LTOLE medication.  
A subject is considered to have taken at least one dose of LTOLE study medication if date of permanent discontinuation of LTOLE study medication is later than the date of the completed LTOLE initiation visit.

## 4.2 Data scopes and censoring rules

The following data scopes will be considered:

- LTOLE follow-up
  - From date of LTOLE initiation visit to last LTOLE follow-up date
- LTOLE treatment emergent
  - From LTOLE initiation visit until last date of drug intake of LTOLE study medication + 2 days
- COMPASS follow-up
  - From randomization until last Follow-up date as defined in section 6.

## 5. Statistical Methodology

All data will be listed and all variables will be summarized by means of descriptive statistics according to their type.

Descriptive statistics such as mean, standard deviation, median, quartiles, minimum, and maximum will be used to summarize continuous variables. Counts and percentages will be used to summarize categorical variables. Event rates, life tables and Kaplan-Meier estimates will be used to summarize time-to-event variables. Graphical data displays may also be used to summarize the data. Confidence intervals calculated similar to the main part of the study will be provided at a 2-sided level of 95% unless otherwise stated.

### 5.1 Population characteristics

The structure of the tables describing population characteristics will closely follow the tables provided for CDB1 but no statistical testing will be used to compare randomized treatment arms. Population characteristics will be displayed for the total of all subjects in LTOLE.

Baseline characteristics have not been collected for LTOLE initiation but at baseline of the COMPASS study. Hence, the data presented will represent the status at baseline of the COMPASS study, which may have been several years before LTOLE initiation.

#### 5.1.1 Sample sizes

Study sample sizes will be tabulated overall for subjects in LTOLE as follows:

- Study sample sizes by region and country

- Study sample sizes by country and site

### **5.1.2 Subject disposition – Overview/Details at visits**

Subject disposition will be presented with focus on the LTOLE related part of the study.

An overview of reasons not participating in COMPASS subjects approached to participate/participate in LTOLE will be given.

An overview of subjects entering LTOLE by randomized antithrombotic and pantoprazole treatment groups will be given. To help understand about the LTOLE entry, Kaplan-Meier estimates for the time from Final Rivaroxaban/Aspirin Follow-Up visit to LTOLE initiation visit will be provided.

A subject is considered as a LTOLE completer if the subject entered LTOLE and completed the LTOLE final visit or died.

A table presenting all subjects who changed study site will be presented including all cases of change of site during the study.

### **5.1.3 Visit and study drug adherence**

The following will be tabulated :

- Number of subjects and reasons for premature permanent discontinuation of LTOLE study medication during LTOLE part
- Number of subjects and reasons for premature permanent discontinuation of LTOLE study follow up, i.e. consent withdrawn or lost to follow-up.

Kaplan-Meier estimates will be used to present

- time to the date of last dose of antithrombotic study treatment (calculated as days from LTOLE initiation visit), and,
- time to last follow-up date

all calculated as date of event – date of LTOLE initiation visit + 1.

Other details regarding visit adherence (e.g., visit completed in person, by telephone, through third party) and completion as well as study drug adherence collected via CRFs will be summarized using frequency tables by visit overall subjects in LTOLE.

In addition, after the final close-out of the study, a bulk batch listing including information of all bulk batches of the study will be provided.

### **5.1.4 Protocol Deviations**

No per protocol analysis set will be defined. The number of subjects with major protocol deviations during LTOLE according to the CRF will be summarized overall. The types of deviations are described in the Data Management Plan.

### **5.1.5 Medical History**

Medical history (recorded at initial randomization visit of the COMPASS study) will be evaluated by frequency tables for subjects in the LTOLE ITT analysis set and the LTOLE Safety analysis set, showing the number of subjects with medical history findings (i.e., listed conditions of previous diagnoses, diseases, or surgeries based on the CRF).

### 5.1.6 Demographics

Demographic data (with baseline defined as baseline of COMPASS study) will be evaluated descriptively for the LTOLE ITT analysis set and the LTOLE Safety analysis set for subjects on LTOLE rivaroxaban/aspirin.

Descriptive statistics (such as mean, standard deviation, median, quartiles, minimum and maximum) will be provided for continuous variables such as

- Age [years]
- Height [cm]
- Weight [kg]
- Waist and hip circumference [cm]
- Body mass index [kg/m^2]

Counts and (appropriate) percentages will be provided for categorical variables such as

- Gender
- Ethnic group and ethnicity/race
- Tobacco use

### 5.1.7 Prior and Concomitant Medication

Frequency tables will be used to summarize the number of subjects with

- relevant antiplatelet agents and anticoagulant between Final Rivaroxaban/Aspirin Follow up visit and LTOLE initiation reported by the subject at the LTOLE initiation visit
- relevant concomitant medications at LTOLE initiation (non-study medications taken regularly for at least 1 month at the time of the LTOLE initiation visit) and at final LTOLE follow up visit: non-study proton pump inhibitor, ACE inhibitor/ Angiotensin receptor blocker (ARB), alpha blocker or other vasodilator, diuretic, lipid lowering agent, calcium channel blocker, beta blocker, Non-steroidal anti-inflammatory drugs (NSAIDs), hypoglycemic agent, selective serotonin reuptake inhibitors (SSRIs).

## 5.2 Efficacy

LTOLE is designed as an open label single arm extension of the COMPASS study. No statistical testings are planned to compare treatment effects and efficacy results will be summarized descriptively with number of subjects with event, crude incidences, and incidence rates, where applicable.

### 5.2.1 Efficacy Variables for LTOLE

The outcome events from the following list will be analysed. For the arrangement of events in LTOLE and not in LTOLE, refer to section 6.1.

- The primary efficacy outcome (composite of myocardial infarction, stroke and cardiovascular death)

- Myocardial infarction
- Stroke
- Cardiovascular death
- Mortality (all-cause)
- Non-cardiovascular death
- Hospitalization
- Hospitalization for cardiovascular reasons

The following reasons for admission will count as cardiovascular reasons:

- Myocardial infarction
- Stroke
- Angina
- Heart Failure
- Venous thromboembolism
- Revascularization
- Amputation
- Resuscitated cardiac arrest
- Severe limb ischemia
- Transient ischemic attack
- Stable angina pectoris
- Cardiac arrhythmia
- Syncope
- Systemic arterial embolism
- Ischemic stroke
- Hemorrhagic stroke
- Uncertain stroke
- Severe limb ischemia
- Venous thromboembolism
- Pulmonary embolism
- Deep vein thrombosis
- Revascularization
- Vascular Amputation
- Angina (unstable, new or worsening)
- Heart failure

- Resuscitated cardiac arrest
- New cancer
- Recurrence of cancer
- GI event
- Overt bleeding of gastroduodenal origin
- Overt upper GI bleeding of unknown origin
- Bleeding of presumed occult GI origin
- Symptomatic gastroduodenal ulcer
- Upper GI Perforation
- Upper GI Obstruction
- Gastrointestinal Pain

### 5.2.2 Efficacy analysis for LTOLE

For the efficacy variables defined in section 5.2.1 in the LTOLE ITT analysis set in the LTOLE ITT data scope the number of subjects with event, crude incidences and incidence rates will be presented.

For all subjects of the ITT set in the COMPASS follow-up data scope, number of subjects with event and crude incidences will be presented. No incidence rates are planned to be presented in this data scope.

### 5.2.3 Subgroup Analyses

The efficacy analyses will be repeated for the following subgroups:

- Coronary artery disease (yes, no)
- Peripheral artery disease (yes, no)
- CAD and PAD (yes, no)
- CAD only, PAD only, CAD and PAD

### 5.3 Pharmacokinetics/Pharmacodynamics

Not applicable.

### 5.4 Safety

#### 5.4.1 Safety Outcome Events for the Antithrombotic Randomization

Safety outcomes of the antithrombotic randomization will be reported with number and percentage of subjects for the LTOLE ITT analysis set as well as the LTOLE Safety analysis set. Incidence in events per 100-patient years will be presented.

For the LTOLE ITT analysis set

- during LTOLE follow-up

- and time from randomization up until LTOLE final follow-up. For this data scope no incidence rates will be presented.

For the LTOLE Safety analysis set, all events from LTOLE initiation up until last LTOLE study drug intake plus 2 days will be presented.

The following safety events will be tabularized:

- Modified ISTH major bleeding
  - Fatal
  - Critical organ bleeding (non-fatal)
  - Requiring re-operation (non-fatal and non- critical organ)
  - Hospitalization (non-fatal, non-critical organ, not leading to re-operation)
  - Gastrointestinal
  - Gastrointestinal (excl. oral cavity and esophagus)
  - Intracranial
- Minor bleeding

The bleeding classification will be assessed via an algorithm. The classification by the algorithm will be used as “adjudicated bleedings” and will be mainly used for safety analyses. In addition the bleedings as reported by investigators will be shown.

### **5.4.2 Other Events of interest**

Other events of interest are:

- Pneumonia
- Clostridium difficile infection
- Other enteric infections
- Fracture
- Gastric atrophy
- Chronic kidney disease
- Diabetes
- Chronic obstructive lung disease
- Dementia

For these events the crude incidence of subjects in the LTOLE ITT analysis set having an event during LTOLE will be presented.

### **5.4.3 Adverse Events**

Summaries of reported adverse events will be provided based on the LTOLE Safety analysis set using the LTOLE treatment emergent data scope as outlined in Section 4.2. The remaining principles of adverse event analyses will be applied as specified in the [SAP](#), version 4.1.

### **5.4.4 Death**

Deaths will be summarized by cardiovascular cause and non-cardiovascular cause

- from randomization to last trial contact (in ITT set)
- from LTOLE initiation to last trial contact (in LTOLE ITT set).

For these data scopes the number of subjects with an event, the crude incidences and the incidence rates will be presented.

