### **3. Study Design**

For the general study design, please refer to integrated SAP, version 4.1.

LTOLE will provide open-label rivaroxaban 2.5 mg bid plus aspirin 100 mg od to COMPASS subjects until it is commercially available or for approximately 3 years from regulatory approval of LTOLE in a country, which ever comes first.

Not all sites who participated in COMPASS also participated in LTOLE. For subjects participating in COMPASS, the follow-up before LTOLE depends on the treatment group: follow-up for the antithrombotic portion ended in 2017 (release data of first clean database 04 AUG 2017), and follow up of pantoprazole/placebo randomization ended in 2018 (relase date of second clean data base 21 SEP 2018). First Patient First Visit for COMPASS LTOLE was achieved on 09 JAN 2018. Hence, patients who had not been randomized to pantoprazole/placebo have not been followed up during the time from close-out of the antithrombotic portion of the trial until they entered LTOLE. On the other hand, subjects randomized to pantoprazole/placebo may have had their final pantoprazole/placebo follow-up visit with or after LTOLE initiation visit. Hence, these subjects have been followed-up continuously.

LTOLE will involve an initiation visit and a follow-up period with follow-up visits every 6 months. The follow-up will be concluded with a final follow-up visit at the end of the study.

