**6. Definitions**

Final LTOLE Follow-up Visit	Final visit at the end of the LTOLE follow-up of the COMPASS trial
Last LTOLE Follow-up Date	
If consent was not withdrawn:  Last LTOLE Follow-up Date                      = first of
 
 
○ date of death (if applicable)
 
○ maximum date of completed Final LTOLE Follow-up visit and last study drug intake, if Final LTOLE Follow-up Visit is completed
 
○ max (dates of visits completed during LTOLE, event dates during LTOLE).
 
 
If consent was withdrawn:  Last LTOLE Follow-up Date                      = first of
 
 
• max (date of death, date of withdrawal, date of confirmed alive)
 
○ maximum date of completed Final LTOLE Follow-up visit (if applicable) and last study drug intake
 

	•
Last rivaroxaban/aspirin Follow-up Date	As defined for CDB1
Last pantoprazole/placebo Follow-up Date	As defined for CDB2
Last Follow-up Date	
If subject is in LTOLE ITT set:  Last Follow-up Date = Last LTOLE Follow-up Date
 
Else If subject is in pantoprazole ITT set:  Last Follow-up Date = Last pantoprazole/placebo Follow-up Date
 
Else If subject is not randomized to pantoprazole/placebo:  Last Follow-up Date = Last rivaroxaban/aspirin Follow-up Date

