### **7. Document History and Changes in the Planned Statistical Analysis**

Version 2 implements analyses with respect to COVID-19 pandemic, updated definition of Last LTOLE Follow-up date due to reported number of patients that reported to take study drug after final LTOLE visit and minor changes for the analyses of prior and concomitant medication.

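### The LTOLE SAP's death rate from randomization spans a gap in follow-up that LTOLE entrants had to survive, so the rate reads too low unless the gap is taken out

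*SAP*

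**What the plan says.** All references are to the LTOLE SAP unless stated.

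- **Section 5.4.4** defines two death summaries. One is "from randomization to last trial contact (in ITT set"), the other "from LTOLE initiation to last trial contact (in LTOLE ITT set"). For both: "For these data scopes the number of subjects with an event, the crude incidences and the incidence rates will be presented".
- **Section 3** says that subjects outside the pantoprazole randomization "have not been followed up during the time from close-out of the antithrombotic portion of the trial until they entered LTOLE". The pantoprazole close-out SAP, Section 5.2.7, says the same.
- **Section 4.1** admits to the LTOLE ITT set only subjects with a completed initiation visit.
- **Section 5.2.2**, on efficacy events from randomization: "No incidence rates are planned to be presented in this data scope". Section 5.4.1 likewise leaves out rates for bleeding counted from randomization.
- **SAP 4.1, Section 4.5.1** defines the last trial contact as the last documented contact with the subject or a third party, survival-status information included.
- **Section 6** sets the Last LTOLE Follow-up Date, where consent was not withdrawn, as the first of three entries: death; the later of final visit and last drug intake, if the final visit was completed; and "max (dates of visits completed during LTOLE, event dates during LTOLE", to which no condition is attached. Section 7 describes the Version 2 change as "updated definition of Last LTOLE Follow-up date due to reported number of patients that reported to take study drug after final LTOLE visit".

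**The concern.** A rate per 100 patient-years needs a denominator in which a death could have occurred and been recorded. For subjects not randomized to pantoprazole/placebo, the gap fails this test. Those who did not enter LTOLE contribute neither time nor deaths in it. Those who did enter contribute time in which, by construction, they could not have died. This is immortal time, and its effect runs one way: the rate falls.

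No section removes the gap. The duration convention in SAP 4.1, Section 6.1.8 (last contact date minus randomization date plus 1) would count it in full if carried over. At stake is a long-term mortality figure for the whole randomized cohort, of a kind that is readily quoted.

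The minor point is of a different type. The third entry in the Section 6 definition can cancel the Version 2 extension to last drug intake for subjects without an event, while leaving it partly active for subjects with one.

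**Working it through.** The plan gives no figure for this point, so there is none to reproduce.

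**Length of the gap.** Inputs: the planned window for the Final rivaroxaban/aspirin Follow-up Visit, end of February to 15 May 2017 (SAP 4.1, Section 4.5.1); a washout call about 30 days later (SAP 4.1, Section 3); first LTOLE visit 09 January 2018 (LTOLE SAP, Section 3).

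- Latest planned close-out: 15 May 2017 + 30 days = 14 June 2017. To 09 January 2018: 209 days, or 209/365.25 = 0.57 years.
- Earliest planned close-out: 28 February 2017 + 30 days = 30 March 2017. To 09 January 2018: 285 days.
- The gap is longer wherever LTOLE opened after 09 January 2018.

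**Effect on the rate.** Let D be observed deaths, T observed person-years and G gap person-years credited to entrants. The rate with the gap is D/(T+G), against D/T without it. The relative shortfall is G/(T+G).

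Cohort sizes are the planning minimums in SAP 4.1, Section 7: 27,400 randomized, 16,440 of them to pantoprazole/placebo, leaving 10,960 (40%).

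The following are assumptions. The only mortality input in the documents is non-CV death of almost 1% per year.

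- All-cause death λ: 1.5% to 3% per year, constant
- Main follow-up m: 2 to 2.5 years, plus 1 year for pantoprazole/placebo subjects, who are taken to have no gap
- Gap g: 0.57 to 1.5 years
- LTOLE entry q, among those alive: 30% to 70%
- LTOLE follow-up L: 1 to 3 years
- No gap deaths captured among non-entrants

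Person-years in each segment equal deaths divided by λ. Central case: λ = 0.02, m = 2, g = 1, q = 0.5, L = 2.

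| Segment | Deaths | Person-years |
|---|---|---|
| Not pantoprazole, main: 10,960 × (1 − e^−0.04) | 429.8 | 21,487 |
| Not pantoprazole, LTOLE: 10,960 × 0.5 × e^−0.06 = 5,161 entrants, × (1 − e^−0.04) | 202.4 | 10,118 |
| Pantoprazole/placebo, main: 16,440 × (1 − e^−0.06) | 957.4 | 47,870 |
| Pantoprazole/placebo, LTOLE: 16,440 × 0.5 × e^−0.06 = 7,741 entrants, × (1 − e^−0.04) | 303.5 | 15,177 |
| Sum | 1,893.1 | 94,652 |

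- Gap time: G = 5,161 × 1 = 5,161 person-years, with no deaths.
- Without the gap: 1,893.1/94,652 = 2.00 per 100 person-years.
- With the gap: 1,893.1/(94,652 + 5,161) = 1.90 per 100 person-years, a shortfall of 5.2%.
- Subjects not randomized to pantoprazole/placebo alone: 632.2/(31,605 + 5,161) = 1.72, a shortfall of 14.0%.

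Over the full grid the overall shortfall runs from 1.6% (λ = 0.03, m = 2.5, g = 0.57, q = 0.3, L = 3) to 11.0% (λ = 0.015, m = 2, g = 1.5, q = 0.7, L = 1), median 4.5%. Among subjects not randomized to pantoprazole/placebo it runs from 4.7% to 27.5%. With the gap removed, the assumed rate is recovered in every scenario.

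**Minor point, the Section 6 date.** Consent not withdrawn, first of read as earliest. Take a final visit on day 1000 that is also the last completed visit, and last intake on day 1030.

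- No later event: the second entry gives 1030, the third gives 1000, so the earliest is 1000. The extension has no effect.
- Non-fatal event on day 1015: the second gives 1030, the third gives 1015, so the earliest is 1015. The event is counted.

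The event is gained without the matching event-free time of other subjects.

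**The case against.** **Death is not like a non-fatal event.** An entrant's vital status through the gap is known, and the death spans end at a contact that includes survival status. The spans in Sections 5.2.2 and 5.4.1 also differ: the first ends at the Section 6 date, and the second is in the LTOLE ITT set. So keeping rates for death is not a formal contradiction. That much stands. It does not rescue the denominator: status through the gap is known for entrants precisely because they survived it, and no follow-up is described for non-entrants. The SAP gives no reason for treating death differently.

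**The size is not documented.** This stands. Entry fraction, mortality and LTOLE duration are assumed, and the cohort sizes are planning minimums. Gap deaths learned of when subjects were approached for LTOLE would reduce the bias. Conversely, Section 3 says only that pantoprazole/placebo subjects may have had their final visit with or after LTOLE initiation, so some of them may also have a gap.

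**Little depends on it.** LTOLE is a single-arm extension with no testing (Section 5.2), and a death rate from LTOLE initiation is also planned. This stands and limits the weight of the point.

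**The Section 6 wording is ambiguous.** SAP 4.1 writes minimum (earliest) elsewhere, so first of could mean the first applicable entry in the list. Under that reading the Version 2 change works. The consent-withdrawn branch fits earliest better, but the wording leaves both open.

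**Readings that go too far.** A reader might infer that the Section 6 date also distorts the death rates. It does not: those spans end at last trial contact, which moves for living and dead subjects alike. A reader might also infer that Section 6 extends follow-up for events only in every case. It does not: completed visits move the date too, and the consent-withdrawn branch lacks the third entry and can run to last intake for a subject later confirmed alive.

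**Conclusion.** The main point holds for one output: the incidence rate of death from randomization in the ITT set. It spans at least about 209 days, by the planned dates, in which subjects not randomized to pantoprazole/placebo were unobserved and LTOLE entrants among them could not have died. Unless the gap is excluded, the rate is too low. The relative size is roughly 2% to 11% overall, conditional on the assumed ranges. The direction does not depend on those ranges, provided that gap deaths among non-entrants are not recovered.

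The counts and crude incidences do not use this denominator. The rate from LTOLE initiation starts after the gap and is unaffected by it. The output is descriptive and carries no test.

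The Section 6 point is separate and minor. It bears on the LTOLE follow-up rates of Sections 5.2.2 and 5.4.1, only where consent was not withdrawn and first of means earliest. Its size cannot be derived from the documents. The time involved is limited to the interval between final visit and last intake, and its effect on those rates is upward.

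**What to change.** 1. **Section 5.4.4.** Drop the incidence rate for deaths counted from randomization and keep the number of subjects and crude incidence. Alternatively, define the denominator as observed segments only: from randomization to the end of rivaroxaban/aspirin or pantoprazole/placebo follow-up, then re-entry at LTOLE initiation. State the choice in a table footnote. The cost is a sentence in the SAP and, for the second option, a small derivation change. One rate is lost or rests on less person-time.
2. **Section 6.** Apply the third entry of the Last LTOLE Follow-up Date only when no Final LTOLE Follow-up Visit was completed, and replace first of by earliest of. Follow-up of completers whose consent was not withdrawn then runs to the later of final visit and last intake, unless death comes earlier, with or without an event. The cost is one condition in the derivation. It credits some event-free time after the visit at which Section 3 says follow-up concludes, so the tables should say so.
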